5.7 SAFETY EVALUATION.....	11
6 STATISTICAL CONSIDERATIONS	12
6.1 PRIMARY ENDPOINT	12
6.2 SECONDARY ENDPOINTS	12
6.3 STATISTICAL METHODS.....	13
6.3.1 Baseline Data	13
6.3.2 Efficacy Analysis	13

STUDY INTERVENTION.....	13
6.4 DESCRIPTION.....	13
6.4.1 Teen-Parent Monitoring Group	13
6.4.2 Teen Only Monitoring Group.....	14
7 SAFETY MANAGEMENT	14
7.1 ADVERSE EVENT REPORTING.....	14
8 STUDY ADMINISTRATION.....	14
8.1 TREATMENT ASSIGNMENT METHODS.....	14
8.1.1 Randomization.....	14
8.2 DATA COLLECTION AND MANAGEMENT	14
8.2.1 Way To Health.....	15
8.2.2 Cellcontrol	16
8.3 CONFIDENTIALITY.....	16
8.4 REGULATORY AND ETHICAL CONSIDERATIONS.....	16
8.4.1 Data and Safety Monitoring Plan	16
8.4.2 Risk Assessment.....	17
8.4.3 Potential Benefits of Study Participation	17
8.4.4 Risk-Benefit Assessment	17
8.5 RECRUITMENT STRATEGY	17
8.6 INFORMED CONSENT/ASSENT	19
8.7 PAYMENT TO SUBJECTS/FAMILIES	20
8.7.1 Payment for time and inconvenience (i.e. compensation)	20
8.7.2 Gifts.....	20
9 PUBLICATION.....	20
10 REFERENCES.....	21

ABBREVIATIONS AND DEFINITIONS OF TERMS

AE	Adverse Event
CHOP	Children's Hospital of Philadelphia
SAE	Serious Adverse Event
UPenn/Penn	University of Pennsylvania
PMACS	Penn Medicine Academic Computing Services
SQL	Structured Query Language
PHP	Hypertext Preprocessor
SSL	Secure Sockets Layer
HTTPS	Hypertext Transfer Protocol Secure
PHI	Personal Health Information

ABSTRACT

Context:

In 2012, 3,328 people were killed and an additional 421,000 were injured in crashes involving a distracted driver¹. Adults aged greater than 40 years old accounted for 44% of these fatalities². Teen driving behavior is heavily influenced by parental driving behaviors with a recent study showing the proportion of teens that text while driving is 14% higher if they have observed their parents doing the same⁴. The proportion of adults who text while driving has recently surpassed teen rates with a 2013 national poll finding 49% of adult car commuters admit to texting while driving, most stating that they did it out of habit⁵. Based on previous findings, it is unlikely that teens will reduce their texting while driving unless their parents do the same.

Objectives:

The objective of this study is to compare measures of acceptance and feasibility across teen-parent dyads randomized to bidirectional teen-parent (teen monitors parent and parent monitors teen) vs. teen only (parent monitors teen) cellphone use while driving.

Study Design:

Research participants will be recruited to take part in a randomized control trial. Participants' cellphone use will be observed during an initial baseline period. Participants will be randomly assigned to one of two conditions (bidirectional teen-parent monitoring or parental monitoring of the teen only). An exit survey and interview will be administered to both the parent and teen separately at the end of the study.

Setting/Participants:

High school students who are age 16 or 17 at the start of the study that drive an average of 4 or more trips per week and hold a valid driver's licenses and a parent for each teen will be recruited. Other inclusion criteria include living with their teen/parent, having their own smartphone (iPhone 4S or newer or Android 4.3 or newer) with data plan, admitting to texting while driving at least once in the past month, and do not currently use a cellphone blocking app or device, parent willing to install device and adjust settings as necessary.

Study Interventions and Measures:

Cellphone blocking device(s) (Cellcontrol DriveID) will be mailed or given directly to participants for each car driven by the teen and/or parent. DriveID will measure all participant cellphone use while the cellphone is in the car for the first three weeks. During

the intervention period, participants will be randomized to one of the two conditions and followed for 8 weeks. Surveys will also be administered as part of this study.

1. BACKGROUND INFORMATION AND RATIONALE

1.1 Introduction

In 2012, 3,328 people were killed in crashes involving a distracted driver; an additional 421,000 people were injured.¹ Adults aged greater than 40 years old accounted for 44% of these fatalities, and drivers under the age of 20 were more likely than any other age group to die in distraction-related crashes caused by cellphone use. According to a CDC survey, 43% of U.S. high school students admit to texting while driving in the last 30 days,² despite the majority knowing that this behavior is harmful.³ It has been well established that teen driving behavior is heavily influenced by parental driving behavior. A recent study demonstrated the proportion of teens that text while driving is 14% higher if they have observed their parents doing the same.⁴ Unfortunately, the proportion of adults who text while driving has recently surpassed teen rates with a 2013 national poll finding 49% of adult car commuters admit to texting while driving.⁵ Most of these adults surveyed said they did this out of habit, despite 98% also knowing it unsafe, and 60% saying they did not do this three years ago.⁵ The emergence of this behavior on a national scale is highly problematic because a meta-analysis of 28 epidemiologic, driving simulator, and naturalistic studies⁶ and a New England Journal of Medicine study⁷ have found that texting while driving increases the risk of crashing by at least 3- to 4-fold. The U.S. Healthy People 2020 objectives call out distracted driving from cellphone use as the top emerging cause of injury in need of future research.⁸

Novel strategies are needed to address this emerging health risk behavior as legal bans, public awareness campaigns, and pledges to not use a cellphone while driving have had little effect on curbing this behavior.⁹ One potential reason these efforts have had limited success is that texting while driving is a behavior shown to be driven by present bias,¹⁰ the tendency to place more weight on benefits realized now and less weight on costs realized in the future, leading to prioritizing immediate pleasure over actions that are in one's long-term interest.¹¹ Several studies motivated by behavioral economic theory have shown that financial incentives reduce health risk behaviors driven by present-biased preferences such as smoking.¹² However, despite great promise, such incentives have not been trialed for combating texting while driving. Furthermore, given the above findings, it is unlikely that teens will reduce texting while driving unless their parents do the same.

1.2 Name and Description of Intervention

Cellcontrol DriveID was released in December of 2013 as a device to overcome a technological barrier in being able to accurately measure whether a driver's cellphone is being used while driving. It is a solar-powered Bluetooth signaling technology placed on the car windshield. DriveID can measure type of cellphone use while driving and be configured to block a driver's cellphone use while the vehicle is in motion. There is no physical interaction with the DriveID device other than installation.

The device is placed on the windshield and an app is downloaded on to the phone. Online configuration of the device settings takes approximately 3-5 minutes. After the initial installation, the device is always on and interacts with the user's cellphone in the background. Only the cellphone with the corresponding DriveID application is monitored by the DriveID device. The DriveID device directly measures the vehicle's movements and can be set to lock the phone at speeds as low as 1 mph. Device setup is flexible to allow specific smartphone applications like navigation and maps to be used if initiated when stopped. The blocking function cannot be deactivated without permission of the account holder.

The study intervention involves randomization into one of two conditions: teen-parent monitoring and teen only monitoring. In the bidirectional teen-parent monitoring condition, the teen driver will receive an automatic notification (via email) when one of his or her parents overrides the DriveID blocking function to use their phone while driving along with the parent receiving a notification when their teen overrides the blocking function. The teen only monitoring condition only involves the parent/guardian receiving a notification (via email) if their teen overrides the DriveID blocking function. Furthermore, if anyone tampers with the DriveID device, delete the corresponding application from their smartphone, or disable Bluetooth capabilities, an email will be sent to a member of the study team.

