4.3.1 Intervention

DriveID will measure participants' trip characteristics (duration, mileage, speed) and cellphone use while the cellphone is in the car in which the DriveID device is installed. DriveID will also record GPS data. This data will not be accessed in real time by the study team and will only be viewed after the completion of the drive.

Coded data on primary and secondary endpoints will be automatically uploaded daily whenever the phone has a Wi-Fi or cellular data connection to the Cellcontrol server and then exported through an encrypted, secure internet connection to Penn's Way to Health IT Platform for management and analysis via linkage of a study ID (as has been established under IRB 14-11234).

After baseline period, parents can view teen trip summaries.

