6.1 Primary Endpoint

In determining feasibility the following endpoints will be measured:

- Proportion of screen eligible who enroll
- Number enrolled per month
- Retention rates by study arm
- Proportion of surveys completed
- Acceptance of cellphone blocking strategy measured on Likert scale in post-study survey

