6.2 Secondary Endpoints

Frequency of phone unlocks at non-zero speeds

Total proportion of trip time the phone is in use at non-zero speeds

Total proportion of trip time on non-call related phone use at non-zero speeds

Total proportion of trip time on call-related phone use at non-zero speeds

Total proportion of trip time on non-call related phone use while stopped.

Total proportion of trip time on call-related phone use while stopped.

Seconds of phone use at non-zero speeds

Seconds of phone use while stopped

Number of incoming calls and texts that were blocked

Number of times participants make or receive a phone call, send or read a text message, and use any application while driving at non-zero speeds

Participant acceptance of cellphone blocking technology based on post-study survey

Incidence of handheld cellphone use and its relationship to incoming text messages and driving conditions

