6.4.1 Teen-Parent Monitoring Group

The blocking settings will turn on by default while driving. Blocking settings will be pre-set to block all incoming calls and text messages while the vehicle is in motion, but participants will have the ability to override the blocking. Number of unlocks can be monitored through logging in to the Cellcontrol website.

In the bidirectional monitoring arm, the teen will receive an email notification when their parent unlocks their phone while driving and vice versa.

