6.4.2 Teen Only Monitoring Group

The blocking settings will turn on by default while driving for both the teen and parent. Blocking settings will be pre-set to block all incoming calls and text messages while the vehicle is in motion, but participants will have the ability to override the blocking. Number of unlocks can be monitored through logging in to the Cellcontrol website.

The teen only monitoring group involves parental monitoring of teen's cellphone use while driving only. The parent will receive an email notification when their teen unlocks their phone while driving. Both parent and teen will drive under the same restrictions, but only the parent will be notified of teen cellphone use.

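### Driving that goes unrecorded after tampering, app deletion or Bluetooth switch-off enters no endpoint or analysis, and because it may differ by arm it can bias the secondary phone-use contrast

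*Combined protocol and SAP*

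**What the plan says.** Recording has two conditions. Section 1.2 states: "Only the cellphone with the corresponding DriveID application is monitored by the DriveID device". Section 4.3.1 limits measurement to "cellphone use while the cellphone is in the car in which the DriveID device is installed". A drive without the app, or outside a fitted car, leaves no data.

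Section 1.2 anticipates that this may be deliberate. If anyone should tamper with the device, delete the app or "disable Bluetooth capabilities, an email will be sent to a member of the study team". No log, follow-up step or analysis rule is attached to that email. The troubleshooting contact in 4.2 concerns installation errors only.

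The arms differ in who learns of a parent's override. In 6.4.1, "the teen will receive an email notification when their parent unlocks their phone while driving and vice versa". In 6.4.2, "only the parent will be notified of teen cellphone use". Participants know their arm (3.2). The documents do not say that the alert to the study team is passed on to the teen.

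The primary endpoints in 6.1 are enrolment, survey completion, acceptance and "Retention rates by study arm". The secondary endpoints in 6.2 include unlock frequency, seconds of use and shares such as "Total proportion of trip time the phone is in use at non-zero speeds". Section 6.3.2 specifies intention to treat and a multilevel model as the likely choice, with no rule for unrecorded driving.

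**The concern.** An unrecorded trip drops out of both the numerator and the denominator of the unlock rate (objective 1 in 2.2) and of the trip-time shares in 6.2. It also lowers raw counts and seconds of use. Intention to treat keeps the person in the analysis but cannot restore the drives.

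A parent in the bidirectional arm can avoid an email to the teen by stopping the recording. A parent in the other arm has no such email to avoid. Deleting the app also removes the blocking that the app performs (3.1.3), so heavier use in hidden driving is plausible, though not shown. The loss of data could then depend both on the randomised condition and on the outcome.

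No listed measure cross-checks the device during the intervention. Self-reported use is listed for the end-of-baseline survey (5.4) but not for the end-of-study survey (5.5).

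Two things are at stake. Section 2 says the study is primarily measuring whether bidirectional monitoring reduces phone use, and 2.2 says the estimates will be used to design the next, fully powered trial. Circumvention by arm is also a feasibility result in its own right, and 6.1 leaves it out.

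**Working it through.** The documents give no disabling rate, use rate, effect size or power, so there is no figure of the plan's own to reproduce. Every input below is assumed, and both arms are given the same true use.

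**1. Some parents stop recording altogether.** Let p be the share of parents who disable and m their use as a multiple of the mean. The mean among those still recorded, relative to the true mean, is (1 − pm)/(1 − p). If teens and parents are pooled in equal numbers with equal mean use, and only parents disable, it is (2 − pm)/(2 − p). The apparent ratio is the bidirectional value divided by the teen-only value (computed unrounded).

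| Assumed p (bidirectional vs teen-only), m | Parents | Pooled dyads |
|---|---|---|
| 10% vs 2%, m = 3 | 0.778/0.959 = 0.811 (19% lower) | 0.895/0.980 = 0.913 (9% lower) |
| 10% vs 2%, m = 2 | 0.889/0.980 = 0.907 (9% lower) | 0.947/0.990 = 0.957 (4% lower) |
| 5% vs 2%, m = 2 | 0.947/0.980 = 0.967 (3% lower) | 0.974/0.990 = 0.984 (2% lower) |

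First row in full: (1 − 0.30)/0.90 = 0.778 and (1 − 0.06)/0.98 = 0.959 for parents; (2 − 0.30)/1.90 = 0.895 and (2 − 0.06)/1.98 = 0.980 for dyads.

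**2. Parents hide some of their hours.** Let h and h0 be the unrecorded share of parents' drive hours in the bidirectional and teen-only arms. Let r be the unlock rate in unrecorded hours divided by the rate in recorded hours, the same in both arms. Recorded rate over true rate is 1/(1 − h + hr), so the apparent ratio is (1 − h0 + h0·r)/(1 − h + hr).

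- h0 = 0, r = 3: h = 5% gives 1/1.10 = 0.91; h = 10% gives 1/1.20 = 0.83; h = 20% gives 1/1.40 = 0.71.
- h0 = 0, h = 10%: r = 2 gives 1/1.10 = 0.91; r = 5 gives 1/1.40 = 0.71.
- h0 = 5%, h = 20%, r = 3: 1.10/1.40 = 0.79.
- Pooled with teens who have equal hours and rates and hide nothing, h0 = 0, r = 3: h = 10% gives (0.90 × 0.833 + 1)/1.90 = 0.92; h = 20% gives (0.80 × 0.714 + 1)/1.80 = 0.87.

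**3. When the bias vanishes or reverses.** With h = h0 or r = 1 the ratio is 1. With r below 1 it exceeds 1: h0 = 0, h = 10%, r = 0.5 gives 1/0.95 = 1.05. Raw counts and seconds of use fall with lost hours even at r = 1.

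**The case against.** A reader might infer that the design does bias the result toward bidirectional monitoring. The documents do not support that. They report no disabling rate, no difference by arm and no link between disabling and use. Blocking applies to parents in both arms, which is a reason to disable in either, and the alert to the study team is the same in both. Unlock counts can also be viewed on the vendor's website in both arms, without a statement of who can log in. The difference in notification makes unequal hiding possible, not established. It concerns parents, since teens' overrides are reported to the parent in both arms.

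A reader might also take 19% as the expected bias. It is a parent-only comparison of raw means, whereas objective 1 compares dyads. Each dyad also has three unblocked baseline weeks (3.1.2), and the likely model in 6.3.2 examines within-subject change. If heavy use is a stable trait, change from baseline removes much of the selection in step 1. It does not remove the bias in step 2, where a person's hidden hours are heavier than the same person's recorded hours, nor that in the raw descriptive summaries.

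A third inference is that someone who disables the app counts as retained with zero use. Section 6.1 does not define retention, and a person with no recorded trips has no denominator for the rates and shares, so is missing rather than low.

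Finally, this is a descriptive pilot, alerts do reach the team, and weekly meetings discuss data issues (8.4.1). All of that is true. A discussion, however, is not a tabulation by arm and does not enter the estimates carried to the next trial.

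**Conclusion.** The concern holds in a conditional form. The plan anticipates circumvention, receives alerts of it and uses them in no endpoint or analysis, while its phone-use endpoints rest on recorded driving alone. Bias toward bidirectional monitoring needs two conditions together: more unrecorded driving in that arm, and heavier phone use in it than in recorded driving. Neither can be judged from the documents.

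Across the disabling scenarios in step 1, the apparent reduction with no true effect runs from 3% to 19% for parents and from about 2% to 9% for pooled dyads, before any gain from analysing change from baseline. These are illustrations, not estimates.

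The possible bias falls on the secondary phone-use endpoints. For the primary feasibility endpoints the fault is omission: circumvention by arm is not among them. Because sign and size are unknown, the events should be counted. The gap does not invalidate the pilot.

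**What to change.** In 6.1, add by arm and separately for teens and parents: the share of participants with at least one tamper, app-deletion or Bluetooth-off alert, and the number of alerts.

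In 6.3.2, report recorded drive hours per week in the intervention period relative to the same person's baseline weeks, in the same breakdown. Trip duration is already measured (4.3.1).

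Also in 6.3.2, add a sensitivity analysis of the unlock rate and the proportion of time in use. Where a person's recorded hours fall short of baseline, assign the missing hours that person's own baseline rate, then a range of multiples of it, stated in advance and including values below and above 1.

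Do not build the analysis on days disabled unless the system also logs re-enabling. Section 1.2 describes an alert when recording is interfered with but none when it resumes, and an alert alone does not show that any driving took place.

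The cost is a log of alerts already received, a few table rows and one further analysis, with no change to participant procedures. The downside is small: recorded hours also fall for innocent reasons such as driving less, so they must be read alongside the alerts.

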1.3 Findings from Non-Clinical and Clinical Studies

The largest, most rigorous study of the crash risk associated with distraction from cellphone use was published in the New England Journal of Medicine in January 2014. The authors conducted two studies on the relationship between the performance of secondary tasks, including cell-phone use, and the risk of crashes and near-crashes. To facilitate objective assessment, accelerometers, cameras, global positioning systems, and other sensors were installed in the vehicles of 42 newly licensed drivers (16.3 to 17.0 years of age) and 109 adults with more driving experience.

During the study periods, 167 crashes and near-crashes among novice drivers and 518 crashes and near-crashes among experienced drivers were identified. The risk of a crash or near-crash among novice drivers increased significantly if they were dialing a cell phone (odds ratio, 8.32; 95% confidence interval [CI], 2.83 to 24.42), reaching for a cell phone (odds ratio, 7.05; 95% CI, 2.64 to 18.83), sending or receiving text messages (odds ratio, 3.87; 95% CI, 1.62 to 9.25), reaching for an object other than a cell phone (odds ratio, 8.00; 95% CI, 3.67 to 17.50), looking at a roadside object (odds ratio, 3.90; 95% CI, 1.72 to 8.81), or eating (odds ratio, 2.99; 95% CI, 1.30 to 6.91). Among experienced drivers, dialing a cell phone was associated with a significantly increased risk of a crash or near-crash (odds ratio, 2.49; 95% CI, 1.38 to 4.54); the risk associated with texting or accessing the Internet was not assessed in this population. The prevalence of high-risk attention to secondary tasks increased over time among novice drivers but not among experienced drivers.

The authors concluded that the risk of a crash or near-crash among novice drivers increased with the performance of many secondary tasks, including texting and dialing cell phones. The study was funded by the Eunice Kennedy Shriver National Institute of Child Health and Human Development and the National Highway Traffic Safety Administration.

There is one previous field study using Cellcontrol's cellphone blocking/filtering technology to reduce cellphone use while driving, which was funded by the National Highway and Traffic Safety Administration (NHTSA Contract DOT HS 811 863) and carried out by investigators at the University of Michigan. The abstract of the full report published online in December 2013 states:

Forty-four participants each received a cell phone filtering/blocking application on their employer-provided cell phones for 9 weeks. During the first and last 3 weeks, cell phone activity including calling, text messaging and application use was simply recorded in the background. During the middle 3 weeks, the cell phone filtering/blocking software was active, meaning that anytime the application sensed that the phone was moving faster than the pre-set speed threshold, all phone activity was blocked. Objective data on participants' phone use behavior and subjective data (from a questionnaire) on participants' acceptance were collected. Additionally, the impact on an organization attempting to implement a similar program employing cell phone filtering/blocking was examined. During the blocking period, participants initiated a higher proportion of their calls when stopped than when the blocking software was inactive. Also, during the blocking period, participants answered a much smaller proportion of incoming calls while driving, and outgoing calls were placed at a lower mean speed. Participants were neutral in their opinions on whether they received a safety benefit from the cell phone blocking.

